Data collection will be conducted at the Northampton VA Medical Center and the West Haven VA Medical Center. Veterans will complete baseline evaluations, and then be given a user ID and instructions to log-on to a study website at home to receive their randomization assignment. Only those who do so will continue in the study and be asked to complete the telephone-delivered assessments on weeks 4, 12, and 24. This randomization after logging in restricts participation to people who demonstrate some motivation and ability to access a website.

Sequence of procedures for the clinical trial:

- Potentially eligible Veterans scheduled for a Compensation examination are identified by reviewing Compensation clinic schedules and charts.
- Potentially eligible Veteran receives letter explaining that a study recruitment telephone call will be coming, thus allowing the Veteran to opt out of receiving it (see Appendix). Veterans can also opt out by calling a toll-free phone provided in the letter.
- Telephone call inviting participation. The Research Assistant calls and asks the Veteran questions to determine eligibility. Following a script (see Appendix), the Research Assistant describes the study to the Veteran and schedules an appointment for informed consent and data collection. Appointments will be scheduled before a Veteran's planned Compensation examination and up to 3 months after the exam. Veterans vary in how able they are to schedule appointments immediately before or after Compensation examinations. Flexible scheduling balances feasibility and experimental rigor.
- Informed consent and baseline data collection by Research Assistant.
- The Research Assistant gives the Veteran a user ID and password to log on to the study Website.
- Veteran goes home, logs onto the website, and receives directions to log-on to either the Benefits Counseling or Control websites (i.e. the Veteran is randomized).
- Veteran is called by the study therapist within two days of logging on and is counseled with the assigned treatment. If the Veteran has not logged on for randomization within a week, then the therapist will call and encourage the Veteran to log-on for randomization and continuation in the study. If after one more week the Veteran has not been randomized, that participant will be discontinued from the study.
- Assessments by phone at weeks 4, 12, 24 (only of randomized Veterans).

B. Remotely-Delivered Benefits Counseling

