- b. The VBA site with fact sheets about the different types of benefits available to Veterans. The topics covered in these fact sheets are: General Benefit Information, Veterans with Service-Connected Disabilities, Veterans with Limited Income, Education and Training for Veterans, Home Loans, Dependents and Survivors' Benefits, Burial and Memorial Benefits, and Insurance.
- c. The VBA websites for the local C&P office where issues pertaining to an individual Veteran's specific application are addressed. The site includes phone numbers to call with questions, e-mail contacts and directions to the VBA office.

3. Role of Therapists in Control Condition: The therapists in the control condition will differ from the Benefits Counseling therapist as shown in the table below

Control Therapist	Benefits Counseling Therapist
Initiate calls to Veterans at weeks 1 and 2	Initiate calls to Veteran at weeks 1 and 2 and around time of Module Three (or thereafter)
Up to three therapy calls of up to 30 minutes each	Up to three therapy calls of up to 30 minutes each
Convey information about Veterans Benefits	Convey information about Veterans Benefits AND vocational issues
Offer to elaborate on information on control websites	Inquiry about modules on Benefits Counseling website. Follow-up inquiries about domains covered on site.

Justification of Sample Size

We estimate that 190 Veterans will be enrolled and complete baseline assessments; 130 will log-in to the randomization site and be assigned to a treatment condition; 104 (52 per condition) will complete at least one follow-up assessment.

Precision Analysis

Consistent with the purpose of a pilot study, the sample size was selected to

estimate the standardized effect of treatment with reasonable precision, rather than to power for a statistically significant effect [50]; A **sample size of 52 per treatment condition** permits estimation of an expected standardized difference in slopes of hours worked between Benefits Counseling and control groups (e.g., (slopeBC-slopeCON)/SDslope) of $\delta=.40$ with a 95% confidence interval of (.01, .79). This effect would reflect an average 6% increase in baseline number of hours worked per month, or a total increase of 43% by month 6. Assuming an average baseline event rate of 40 hours/28 days and no change in the control group, this effect is equivalent to approximately 17 additional hours (approximately 2 days) of work per month by month 6.

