does not record how long was spent on the website because it cannot distinguish between when someone is using the program, has left the browser open, or has left the program without logging out. Study therapists will complete a contact log for each encounter. The contact log will document whether there was a scheduled contact that was not attended, the date and time of contact, and time spent in minutes.

End of Study Measures

1. The current diagnoses, service-connection outcome, and award determination will be obtained from the completed Compensation and Pension examination and VBA database. Diagnoses will be coded within DSM-V with specifiers for definite diagnoses and rule-outs.
2. VA Service Use Outcomes. Analyses will be conducted by [name], a national authority on service use analyses. Episodes reflecting use of VA substance abuse, specialized PTSD and other mental health treatment will be collected from VA administrative records as described previously [73, 74]. Information will be accessed by an agreement between the MIRECC and the West Haven-sited Northeast Program Evaluation Center (NEPEC), which routinely accesses this information for VA reports. VA bed section codes indicate hospitalization on specialized units and VA clinic codes indicate outpatient treatment in specialized clinics. Mental Health service use data will be collected from 24 weeks before the Compensation examination (to allow analyses to control for baseline service use) until 24 weeks after claims adjudication.
3. Cost of Therapist Time Providing the Intervention: The direct costs of providing Remotely-Delivered Benefits Counseling will be calculated but a full cost-effectiveness analysis is beyond the scope of this proposal. The amount of time the therapist spends will be calculated by having therapists maintain logs of time spent on study-related activities including conducting telephone calls, scheduling phone calls, and reminding Veterans to access the study website. The product of the therapist's time spent and the average therapist cost will be used to calculate the labor cost. Therapist salaries will be calculated including fringe benefits but not the overhead rate of the VA facilities. We will not include research costs, facility costs, or the costs of developing the intervention.

Data Analysis

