In the clinical trial, assessment for adverse events will be a routine part of every study and therapy visit. Any report that a patient required overnight treatment in any facility (emergency room, detoxification, and hospitalization) will constitute an SAE, as will any report of death or serious disability. Hospitalization or death of another individual due to direct action of patient will also be considered an SAE.

Any SAEs will be immediately reported to [name] and, if he is unavailable, to [name]. Reports to [name] will include a description of the event and a summary of recent contacts with the patient. This summary will include any warning signs of the adverse event, the patient's general state and any information suggesting a causal link between study participation and the event. [name] will report these to the IRB within 3 working days.

The New England MIRECC's D.S.M.B. will be the D.S.M.B. for this study. The D.S.M.B. will be contacted within 3 days about all significant study-related adverse events. The main risks of the study are frustration with the study procedures, frustration with the Benefits Counseling website, and someone learning about the Veteran accessing the Benefits Counseling website without the Veteran's permission. Because of the very low risk that either therapy would worsen outcomes, no a priori stopping criteria are proposed. Every year, [name] and the D.S.M.B. will review study information on a standardized form. Board members will review recruitment, retention, and follow-up rates for the study-to-date, SAEs and AEs and other data as the D.S.M.B. deems necessary.

Based on this report, each DSMB member will complete a form making one of two recommendations: 1) continue recruitment as planned; or 2) schedule formal DSMB meeting immediately. If any DSMB member recommends a meeting, this will be scheduled within one week, minutes will be kept, the report will be reviewed with the PI, and the committee will vote on whether the study should: 1) continue recruitment unchanged; 2) continue with a protocol amendment; 3) stop recruiting pending further investigation. If, after this meeting, any DSMB member votes to stop recruitment or requests a protocol modification, the Yale IRB will be informed.

A written summary including this information will be provided to the IRB with the protocol renewal.

D. Potential Benefits

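### SAE detection rests on study and therapy contacts, 20% of randomized Veterans are expected to complete no follow-up assessment, and the planned VA service-use extract is not reconciled with SAE reports

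*Combined protocol and SAP*

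**What the plan says.** - **How events are found.** Under Data Safety Monitoring Plan, 2. Safety Monitoring Plan, "assessment for adverse events will be a routine part of every study and therapy visit". The definition follows: "Any report that a patient required overnight treatment in any facility (emergency room, detoxification, and hospitalization) will constitute an SAE". Death and serious disability also count. The investigator "will report these to the IRB within 3 working days", and the DSMB reviews SAEs and AEs yearly.
- **Who is expected to be followed.** Under Justification of Sample Size, "130 will log-in to the randomization site and be assigned to a treatment condition" and "104 (52 per condition) will complete at least one follow-up assessment". Phone assessments are at weeks 4, 12 and 24.
- **Therapist calls.** Both arms allow up to three therapy calls. The table under Role of Therapists in Control Condition has control therapists initiating calls at weeks 1 and 2. Benefits Counseling therapists do the same and also call around Module Three or later. The description of the Session-Three call adds a therapist call at week 12 if the Veteran has not called, and calls at weeks 16 and 20 while the claim decision is pending.
- **Record data.** Under End of Study Measures, 2. VA Service Use Outcomes, "Episodes reflecting use of VA substance abuse, specialized PTSD and other mental health treatment will be collected from VA administrative records". Bed section codes identify stays on specialized units. The Schedule of Assessments places this extract at end of study. No section connects it with SAEs.
- **Veterans who cannot be reached.** Participant Tracking Procedures lets staff open VA records for contact details, appointments and likely locations, subject to an opt-out. It mentions no check for admissions.

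**The concern.** A Veteran who answers no call gives no report, so an overnight stay can pass unseen. An admission may also be the reason a call is missed. If so, the missing reports would not be a random sample, although the documents offer no evidence either way.

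The schedule of staff-initiated calls adds a second difficulty. A control Veteran who completes no assessment has no staff-initiated therapy call specified after about week 2 of 24. A comparable Benefits Counseling Veteran may be called at weeks 12, 16 and 20. With equal assessment follow-up, the arms would still have unequal opportunity to report an event.

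What is at stake is the meaning of the SAE count. The plan calls the risk low but greater than minimal and sets no stopping criteria in advance, so the yearly DSMB review carries much of the safety oversight. Unless completeness of contact is shown by arm, a low count cannot be told apart from few contacts.

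**Working it through.** **1. The plan's own flow.** Inputs from Justification of Sample Size: 130 randomized, 104 with at least one follow-up assessment.
- No follow-up assessment: 130 − 104 = 26, and 26/130 = 20.0%.
- Check: 104/(1 − 0.20) = 130, so the plan's figures are consistent.

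**2. What the 20% measures.** It is the share with no follow-up assessment, not the share with no contact.
- Therapy calls are also AE contacts. If a share s of the 26 have no therapy call either, the share never reached is 26s/130: 0% for s = 0, 10% for s = 0.5, 20% for s = 1.
- In the other direction, the 104 need only one of three assessments, so part of the 24 weeks may be unobserved for some of them too.

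**3. Illustration of size.** The documents give no admission rate. I assume a 24-week risk r of overnight admission between 2% and 20%. For m Veterans with no AE contact, the expected number with an unseen admission is m × r, and P(at least one) = 1 − (1 − r)^m.

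| r (assumed) | m = 26: expected | m = 26: P(≥1) | m = 13: expected | m = 13: P(≥1) |
|---|---|---|---|---|
| 2% | 0.5 | 0.41 | 0.3 | 0.23 |
| 5% | 1.3 | 0.74 | 0.65 | 0.49 |
| 10% | 2.6 | 0.94 | 1.3 | 0.75 |
| 20% | 5.2 | 0.997 | 2.6 | 0.95 |

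m = 26 means that no therapy call reaches any of the 26. m = 13 means that half have calls covering the period.

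**4. If the unreached have higher risk.** With an assumed risk ratio RR for unreached against reached, none of the 26 reached and full capture among the 104, the share of admissions missed is 26RR/(104 + 26RR).
- RR = 1: 26/130 = 20%
- RR = 2: 52/156 = 33%
- RR = 3: 78/182 = 43%

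These are not bounds. Therapy calls would lower them, and missed assessments among the 104 would raise them.

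**5. Does the extract reach week 24?** Its window closes 24 weeks after claims adjudication. If a claim is decided k weeks before randomization, the window closes at study week 24 − k. This can happen: the baseline visit may fall up to 3 months after the Compensation examination, and log-on for randomization may take about two further weeks. As written, coverage to week 24 is not assured for every Veteran.

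**6. What the extract can recover.** SAEs include overnight treatment in any facility. The extract holds VA mental health and substance abuse episodes only. The documents do not give the share of SAEs in that subset.

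**The case against.** The strongest reply is that asking at every contact is a coherent method for low-risk counseling, and that record reconciliation is an enhancement. The documents do not contradict themselves here. Several stronger readings that a reader might infer also fail:

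- **That SAEs can come only from completed contacts.** The definition accepts any report without limiting its source, and the tracking look-up in VA records could bring an admission to light. What stands is that no procedure is written to generate such a report.
- **That the 26 are never contacted.** Therapy calls may reach some of them.
- **That the VA extract would capture all their admissions.** It omits general medical and non-VA stays. The Background cites a study in which 75.3% of Veterans presenting for Compensation examinations had not received VA services before, and the section on participant payments says many have no VA treatment relationship. The yield may be small. That the extract covers every randomized Veteran is a reasonable reading of an administrative source, but it is not stated.
- **That a planned between-arm SAE comparison is biased.** None is planned. The DSMB sees retention and follow-up figures with the SAEs, and no stopping rule depends on the count.
- **That the extract could support prompt reporting.** It is scheduled for end of study.

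These points narrow the claim. They leave the absence of a written safeguard for Veterans not reached, the later staff-initiated calls in one arm, and the lack of any link between the extract and SAEs.

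**Conclusion.** The point holds in limited form. The plan describes no active SAE source beyond study and therapy contacts, expects 20% of randomized Veterans to complete no follow-up assessment, and schedules staff-initiated therapy contact later in one arm. Admissions among Veterans not reached may go unreported, and any tabulation of SAEs by arm could partly reflect contact.

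The number missed cannot be derived from the documents. The illustrative range, from 0.3 expected (2% risk, 13 Veterans without contact) to 5.2 (20% risk, 26 without contact), rests on assumed risks and assumed therapy contact. A reader might infer that a fixed 20% to 43% of admissions will be missed. The documents support no such figure.

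The plan should still be changed, because the data are already to be collected and the final SAE count would depend less on who was reached. No design figure changes.

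**What to change.** Add to the Safety Monitoring Plan:

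1. For every randomized Veteran, reached or not, overnight VA mental health and substance abuse admissions from randomization to week 24 are taken from the service-use extract. Its window is extended to at least week 24 where 24 weeks after adjudication falls earlier.
2. Records are linked by study ID before identifiers are removed. The section on Confidentiality of Research Materials plans that removal once service-use data are extracted.
3. Record-based admissions are merged with reported SAEs without double counting. They are tabulated by arm over all randomized Veterans, showing the source (report or record) and the completeness of contact by arm.
4. Non-VA and general medical stays are stated to depend still on report.
5. This is stated to be an end-of-study reconciliation. It does not replace the 3-working-day report to the IRB and does not inform the yearly DSMB form unless the query is rerun for it.

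The cost is modest: a possibly longer extract window, a linkage arranged in advance, one merge and one table. The downsides are partial recovery, because many of these Veterans may have little VA care, and a possibly higher SAE count. Contact schedules and clinical procedures stay as they are.
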